3. PROTOCOL SUMMARY

3.1 Synopsis

Steering Committee	[name], UNIVR					
	[name], UNIVR					
	[name], UNIVR					
	[name], UNIBO					
	[name], AP-HP					
	[name], INSERM					
	[name] / [name], UHC					
	[name], UMCG					
	[name], SAS					
	[name], RER-ASSR					
	[name], FCRM					
	[name], REG VEN ([name], Az. Zero)					
	[name], UANTWERPEN [name], UMGC					
	[name], PENTA					
	[name], UNIFESP, Brazil					
	[name], UBA, Argentina					
	[name], THSTI, India [name], CBCI, India					
Principal investigator	[name], UNIVR					
Co-principal investigators	[name], UNIVR					
Study design	Multicenter, observational, prospective cohort study enrolling hospitalized and non-hospitalized patients with a diagnosed SARS-CoV-2 infection.					
Study population	Patients of all age and any comorbidity with previous diagnosis of SARS-CoV-2 infection admitted to or treated as inpatients or outpatients in university and non-university hospitals or medical practices.					
Inclusion criteria	Any age					
	Any comorbidity					

	Laboratory confirmed SARS-CoV-2 infection by PCR diagnosis from nasopharynx, oropharynx, bronchoalveolar lavage, stool, or blood. Rapid tests are an acceptable alternative.				
	Person (or attorney or deputy who has been author- ized to make the decision for patients who lack ca- pacity) consent to participate				
Exclusion criteria	Lack of consent to participate				
ORCHESTRA Partners	Università degli Studi di Verona (UNIVR);				
	Alma Mater Studiorum – Università di Bologna (UNIBO);				
	Institut National de la Sante et de la Recherche Me- dicale (INSERM);				
	Servicio Andaluz de Salud (SAS);				
	Consorzio Interuniversitario (CINECA);				
	Luxembourg Institute of Health (LIH);				
	Assistance Publique Hopitaux de Paris (AP-HP);				
	Regione Emilia Romagna (RER-ASSR);				
	Fundacion Privada Instituto de Salud Global Barce- lona (ISGLOBAL);				
	Ludwig-Maximilians-Universitaet Muenchen (LMU MUENCHEN);				
	Universiteit Antwerpen (UANTWERPEN);				
	Helmholtz Zentrum Muenchen Deutsches For- schungszentrumfuer Gesundheit und Umwelt GMBH (HMGU);				
	Klinikum der Universitaet zu Koeln (UHC);				
	Fondazione PENTA – for the treatment and care of children with HIV and related diseases - ONLUS (PENTA);				
	Universitaet Stuttgart (USTUTT);				
	Centre de Recherches Medicales DE Lambaréné (CERMEL);				
	Regionalny Urad Verejneho Zdravotnictva so si- idlom v Banskejbytrici(RAPH BB);				
	Charité – Universitaetsmedizin Berlin (CHARITÉ);				
	Academisch Ziekenhuis Groningen (UMCG);				

	Centre Informatique National de l'Enseignement Superieur (CINES);
	Universidad de Oviedo (UNIOVI);
	Universidad de Buenos Aires (UBA);
	Institutul National de Sanatate Publica (INSP);
	Regione del Veneto (REG VEN);
	Fondation Congolaise pour la Recherche Medicale (FCRM);
	Translational Health Science and Technology Insti- tute (THSTI), Faridabad, Haryana, India;
	Catholics Bishops Conference of India, Society for Medical Education (CBCI), Bangalore, India;
	Escola Paulista de Medicina -Universidade Federal de São Paulo, Brazil.
Study rationale	The present study aims at harmonising follow-up strategies across the participating cohorts to allow a standardized collection of data on characteristics and determinants of COVID-19 long-term sequelae.
Primary objective	To describe characteristics of COVID-19 sequelae, including type, rate, and length through clinical, la- boratory, and radiological assessments
	To investigate valuable, confounder-adjusted, asso- ciations between COVID-19 sequelae and COVID- 19 severity, comorbidities, aetiology (SARS-CoV-2 variants), COVID treatment (including monoclonal antibodies), and trends in SARS-CoV-2 antibodies
	To describe the rate, the aetiology (SARS-CoV-2 variants), severity, and clinical determinants of COVID-19 re-infections
Secondary objective	To compare the time course of the immunological re- sponse of the population with sequelae with the im- munological response of the population without se- quelae.
	To investigate immunological patterns related to spe- cific long-term sequelae.
	To investigate possible associations of SARS-CoV-2 variants with COVID-19 severity, time course of the immunological response, and long-term sequelae.

	To describe the rate and severity of sequelae and im- munological trends of COVID-19 in patients vac- cinated against SARS-CoV-2.
	To describe the time course of intestinal and pulmo- nary microbiome after SARS-CoV-2 infection.
	To investigate possible associations of long-term se- quelae with hypercoagulability
	To describe the relationship between risk perception and adherence to preventative measures over time, including vaccine acceptance.
	To describe the use of health care services among SARS-CoV-2 patients.
	To describe the relationship between risk perception of reinfection and the adherence to preventative measures over time after the SARS-CoV-2 infection, including vaccine acceptance.
	To describe the use of health care services among pa- tients recovered from SARS-CoV-2.
	To identify human and viral genetic markers indica- tive of disease severity by doing genetic and epige- netic analysis in COVID-19 patients.
Time schedule	Patients will be followed-up for up to 18 months af- ter the SARS-CoV-2 infection diagnosis.

3.2 Schedule of assessments (SoA)

Table 1 - Schedule of follow-up Assessments

	COVID-19 (2 weeks ¹ ± 2 weeks)	3 months ¹ ± 1 month	6 months ¹ ± 1 month	12 months ¹ ± 1 month	18 months ¹ ± 2 months
Screening/baseline					
Inclusion criteria ¹					
Demographics ²					
Healthcare setting ³					
Length of hospital stay, days					
ICU admission					
Medical history ⁴					
Treatment					
Comorbidity management ⁵	Х	Х	Х	Х	Х
Anti-COVID therapy ⁶	Х				
Antibiotic therapy ⁷					

Oxygen therapy ⁸	v	X*	X*	X*	X*				
SARS-CoV-2 vaccination ⁹	X X	X	X	X	X				
Clinical assessment	Λ	Λ	Λ	Λ	Λ				
Relevant medical new events ¹⁰	Х	Х	X	Х	Х				
COVID-19 symptom ¹¹ onset	X	Λ	Λ	Λ	Λ				
		V*	V*	V*	V*				
COVID-19 symptom end	X	X*	X*	X*	X*				
COVID severity ¹²	X X								
SOFA score		37	37	37	37				
Vital signs ¹³	X	X	X	X	X				
Physical examination ¹⁴	Х	X	X	X	X				
12-lead electrocardiography	X	X	X	X	X				
6-minute walking test	Х	Х	Х	Х	Х				
DLCO (diffusing capacity for car- bon monoxide)	Х	Х	Х	Х	Х				
Pulmonary function test ¹⁵	Х	Х	X	Х	X				
Questionnaires									
Functional status ¹⁶	Х	Х	Х	Х	Х				
Respiratory impairment ¹⁷	Х	Х	X	Х	Х				
Mental health ¹⁸	Х	Х	X	X	Х				
Perceived risk of re-infection/ad-									
mission/re-admission ¹⁹	Х	Х	Х	Х	Х				
Adherence to main preventative	Х	Х	Х	Х	Х				
non-pharmacological measures ²⁰	Λ	А	А	А	Λ				
SARS-CoV-2 vaccination: ac-									
ceptance/non-acceptance and rea-	Х	Х	Х	Х	Х				
sons ²¹									
Imaging									
Lung ultrasound	Х	X	X*	Х	X*				
X-ray	Х	Х	X*	X*	X*				
High-resolution CT scan	Х	Х	X*	X*	X*				
Cardiac ultrasound	Х	Х	X*	Х	X*				
Cardiac MRI ²²	X^{21}	X^{21}	X*	X^{21}	X*				
Biochemistry									
Blood tests ²³	Х	X	X*	Х	X*				
Arterial blood gas test	Х	х	X*	X*	X*				
(pO ₂ /pCO ₂ /pH)									
Urine tests ²⁴	Х	X	X*	Х	X*				
Immunology			1						
Immune - serology and type I IFNs autoantibodies	Х	Х	X	Х	Х				
Immune - cytokine and chemokine	Х	X ³⁵	X 35	X ³⁵	X *				
Immune - cellular	X	X 35	X 35	X 35	X *				
Microbiological tests-NP swabs	11								
Viral variant and metagenomics									
sequencing	Х	X*,34	X*,34	X*,34	X*				
EDTA whole blood									
Genetic and epigenetic analysis	Х	X	X	Х	Х				
Stool Sample (faeces or rectal									
swab)									
Metagenomic sequencing	Х		Х		Х				
	unctive variable	s for specific fr		ns					
HIV									
HIV-infection status ²⁵	Х	Х	X	X	Х				
HIV-Infection therapy 26	X	X	X	X	X				
Assessment of adherence to fol-	4 8								
low-up visits and antiretroviral	Х	Х	X	Х	Х				
therapy	-		_	-	-				
1.2		1	1	ı					

Elderly					
Cognitive status ²⁷	Х	Х	Х	Х	Х
Pregnant women/new mother					
History of positive SARS-CoV-2					
molecular test on amniotic fluid or					
breast milk ²⁸					
History of detection of micro-					
thrombotic disease on placenta tis-					
sue or umbelical cord tissue					
Children					
History of positive SARS-CoV-2					
molecular test on amniotic fluid or					
breast milk ²⁸					
Biometric paramethers ²⁹	Х	Х	Х	X	Х
Transplant					
Transplant general information ³⁰					
Graft function ³¹	Х	Х	Х	Х	Х
Immunosuppressive regimen ³²	Х	Х	Х	Х	Х
Onco-haematology					
Assessment of adherence to onco-	Х	х	X	х	х
logic follow-up visits and therapy	Λ	Λ	Λ	Λ	Λ
Assessment of progression of the	Х	X	x	х	х
disease and relapse	Λ	Λ	Λ	Λ	Λ
Assessment of adverse events ³³	Х	Х	Х	Х	Х

Footnotes

Modular data capture according to level of commitment (level I, level II, level III).

Level I	Assessments in level I are mandatory
Level II	Customized according to the feasibility of each cohort

- * Reassessed only if outside the normal ranges at the previous assessment or if clinically indicated
- 1. Day 0: first positive SARS-CoV-2 test
- Demographics: age (years), sex, ethnic group (African, Asian, European, Latin America...), education (no formal education, lower than college, college or higher), cigarette smoking (never-smoker, former smoker, current smoker), usual residence (home, long-term care facility, public dormitory, prison, homeless), current occupation (student, unemployed with no benefits, unemployed with benefits, employed, self-employed, informal worker)
- 3. Healthcare setting: (a) outpatient (b) non-intensive care unit (c) intensive care unit.
- 4. Medical history: cardiovascular diseases (hypertension, coronary artery disease, congestive heart failure), diabetes (without insulin, with insulin), chronic respiratory disease (asthma, chronic ob-

structive pulmonary disease, obstructive sleep apnoea, restrictive lung disease, pulmonary hypertension), kidney disease (chronic with/without dialysis), liver disease other than cancer (HBV/HCV/HDV chronic viral hepatitis, other chronic disease, cirrhosis), metabolic disease, immunosuppressive conditions (solid organ transplant recipient, auto-immune diseases), cancer (solid cancer, haematological malignancies, type of primitive cancer/haematological malignancies, presence of metastases, if ongoing chemotherapy), mental or neurological disorders (psychiatric illness, anxiety disorder, mood disorder, psychotic disorder, Alzheimer disease, dementia other than Alzheimer, Parkinson's disease, myasthenia gravis, epilepsy, stroke (with/without residual deficits, neuromuscular disease, multiple sclerosis), muscular dystrophy, amyotrophic lateral sclerosis); TB co-infection; other opportunistic co-infection (specify) for HIV population

- 5. Comorbidity management: drug name and dose (to include only treatments taken regularly)
- 6. Anti-COVID therapy: drug name, maintenance dose, and duration
- 7. Antibiotic therapy: drug name, dose, duration, and type of treated infection
- Oxygen therapy: nasal prongs, face mask, face mask with reservoir, high-flow nasal cannula, noninvasive ventilation, mechanical ventilation; numbers of O₂ (L/min) provided (maximum reached) and fraction of inspired O₂ (FiO₂) provided (maximum reached)
- 9. SARS-CoV-2 vaccination: vaccine name, date of administration
- Relevant new medical events or worsening of previous conditions, including deep venous thrombosis, pulmonary embolism, infections (including a new SARS-CoV-2-infection during follow-up), malignancies (type of cancer, overall stage).
- 11. Symptoms: abdominal pain, ageusia/dysgeusia, anosmia, balance impairment, behaviour disorder, chest pain or chest tightness, confusion, cough, delirium, diarrhoea, disrupted sleep, dizziness, dysp-noea, fatigue, fever (including low-grade fever), headache, hypothermia, impaired cognitive status, lethargy, loss of appetite, mood affective disorder, myalgia, nausea/vomiting, palpitation, phlegm, runny nose, sore throat, stuffed nose, syncope, wheeze.
- 12. WHO Clinical Progression Scale
- 13. Vital signs: dead/alive, blood pressure, body temperature, heart rate, respiratory rate, peripheral oxygen saturation
- 14. Physical examination: BMI, abdominal examination, pulmonary examination, cardiac examination, neurological examination, peripheral vascular examination
- 15. Pulmonary function test: FEV₁, FVC, FEV₁/FVC, TLC, FRC, RV
- Questionnaires to address the functional status: Post-COVID-19 Functional Status (PCFS) Scale, Global Physical Activity, Questionnaire (GPAQ), Barthel Index, Medical Outcome Study Short

Form (MOS SF)-36 Score, EuroQol five-dimension five-level (EQ-5D-5L) questionnaire, Clinical Frailty Scale (CFS), Basic Activity of Daily Living (BADL).

- Questionnaires to address the respiratory impairment: Saint George Respiratory Questionnaire (SGRQ), Transition Dyspnoea Index (TDI), mMRC (Modified Medical Research Council) Dyspnea Scale
- Questionnaires to address the mental health: Hospital Anxiety and Depression Scale (HADS), Kessler Psychological Distress Scale (K10), Impact of Event Scale – Revised (IES-R), Resilience Scale for Adults (RSA)
- 19. Perceived risk of re-infection on a scale 0-10 (no risk- very high risk); perceived risk of admission/re-admission on a scale 0-10 (no risk- very high risk)
- 20. Frequency mask-wearing (type of mask); frequency hand washing; respect of social distance; avoidance of social gathering
- 21. Was the vaccine accepted? Why not accepted (lack of trust in efficacy and/or safety; not useful in the specific case; prefer someone else gets it before me)
- 22. Cardiac MRI only if abnormal cardiac ultrasound
- 23. Blood tests: White blood cell count, lymphocyte count, neutrophil count, platelets, sodium, potassium, creatinine, glucose, bilirubin, alanine aminotransferase, aspartate aminotransferase, gamma glutamyl transpeptidase, albumin, lactate dehydrogenase, ferritin, creatine kinase, fibrinogen, INR, partial thromboplastin time, D-dimer, NT-pro-BNP, troponin, C-reactive protein (CRP), procalcitonin, venous lactate
- 24. Urine tests: pH, concentration, protein, glucose, red blood, white blood cell count
- 25. CD4 lymphocyte count; HIV-viral load; AIDS status
- 26. HIV-therapy: drug name and dose (only ongoing treatment); previous switch to other regimens for virological failure
- 27. Questionnaires to address cognitive status: Cognitive Failure Questionnaire (CFQ), Mini-Mental State Examination, Clinical Dementia rating Scale, Montreal Cognitive Assessment (MOCA).
- 28. Results of SARS-CoV-2 molecular test on amniotic fluid
- 29. Weight, height/length, cranial circumference, BMI
- 30. Type of transplant (hearth, lung, kidney, liver, pancreas); single-combined; year of transplantation
- 31. Graft function: good, impaired, failure, rejection acute-chronic, recurrence of underlying disease, other
- 32. Immunosuppressive regimen: drug name and dose
- 33. According to Common Terminology Criteria for Adverse Events (CTCAE)

- At least one of three timepoints (month 3, month 6, month 12) is required to perform metagenomics analysis.
- 35. At least one of the three timepoints (month 3, month 6, month 12) is required.

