8. OBJECTIVES

Main objectives of the study are:

- To describe characteristics of COVID-19 sequelae, including type, rate, and length through clinical, laboratory, and radiological assessments
- To investigate valuable, confounder-adjusted, associations between COVID-19 sequelae and COVID-19 severity, comorbidities, aetiology (SARS-CoV-2 variants), COVID treatment (including monoclonal antibodies), and trends in SARS-CoV-2 antibodies
- To describe the rate, the aetiology (SARS-CoV-2 variants), severity, and clinical determinants of COVID-19 re-infections

Furthermore, data retrieved from COVID-19 cohorts will address the following objectives:

- To compare the time course of the immunological response of the population with sequelae with the immunological response of the population without sequelae.
- To investigate immunological patterns related to specific long-term sequelae.

- To investigate possible associations of SARS-CoV-2 variants with COVID-19 severity, time course of the immunological response, and long-term sequelae.
- To describe the rate and severity of sequelae and immunological trends of COVID-19 in patients vaccinated against SARS-CoV-2.
- To describe the time course of intestinal and pulmonary microbiome after SARS-CoV-2 infection.
- To investigate possible associations of long-term sequelae with hypercoagulability
- To describe the relationship between risk perception of reinfection and the adherence to preventative measures over time after the SARS-CoV-2 infection, including vaccine acceptance.
- To describe the use of health care services among patients recovered from SARS-CoV-2.
- To identify human and viral genetic markers indicative of disease severity using WGS or WES followed by functional analysis of the most promising variants.

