13. STATISTICAL ANALYSIS

Sample size calculation. The number of inclusions will depend on the progress of the SARS-CoV-2 pandemic, which is unknown at this time. Therefore, the number of patients who will be included cannot be determined in advance. However, depending on the timing of the project and the included cohorts, the expected enrollment is 10000 subjects.

We will carry out comprehensive descriptive analyses taking into account sociodemographic factors and clinical courses. The frequency distributions of the characteristics will be given in absolute and relative numbers, median plus interquartile range (IQR) or mean values plus 95% confidence interval (CIs). Associations with specific treatment strategies, disease severity patterns and laboratory results will be analysed using chi-square tests, t-tests or Mann-Whitney tests, depending on the data. To evaluate potential risk factors, multivariate regression models will be carried out. Outcome time analyses using Cox proportional-hazards regression models with time-dependent covariates will be performed to examine

factors associated with each endpoint (including death). In addition, we will use cumulative incidence functions, such as the Fine-Gray subdistribution hazard regression model, to account for competing events (i.e., relocation, discharge against medical advice, etc.). For missing values, a different strategy to understand the causes and the significance for the analysis will be developed and a graduated procedure for dealing with censorship and imputations via linked regressions will be developed. The significance level is defined with a p-value <0.05. All statistical analyses will be carried out with STATA, Python and/or R statistics software by trained staff (epidemiologists, statisticians) using the latest analysis methods.

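### Anti-COVID therapy is specified without a start date, so treatment cannot be placed on the Day 0 time axis, and ever-treated coding from Day 0 would bias treatment associations

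*Combined protocol and SAP*

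**What the plan says.** Section 3.2, Table 1, footnote 6 describes the treatment variable as "Anti-COVID therapy: drug name, maintenance dose, and duration". Table 1 marks it at one visit only, headed "COVID-19 (2 weeks ¹ ± 2 weeks"), which spans Day 0 to week 4. Footnote 1 sets the time origin: "Day 0: first positive SARS-CoV-2 test". Footnote 9, by contrast, asks for "SARS-CoV-2 vaccination: vaccine name, date of administration". No start or stop date for anti-COVID therapy appears elsewhere in the text supplied.

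Section 8 makes the confounder-adjusted association of sequelae with "COVID treatment (including monoclonal antibodies") a main objective, and another main objective covers how long sequelae last. Section 12 has participants score symptoms every day so that symptom length can be measured.

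Section 13 plans "Cox proportional-hazards regression models with time-dependent covariates" to study "factors associated with each endpoint (including death"). It lists neither the time-dependent covariates nor the endpoints other than death. For associations with treatment strategies it names two-group tests (chi-square, t, Mann-Whitney).

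**The concern.** Duration says how long a treatment lasted, not when it began. Two patients with five days of the same drug, one starting on day 1 and the other on day 12, have the same record. Recovery can be dated to the day while the exposure cannot be dated at all.

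A patient must still be ill and alive to start treatment some days after Day 0. If everyone ever treated is counted as treated from Day 0, those guaranteed event-free days are credited to treatment. This is immortal-time bias. For symptom resolution it makes an inert drug look as if it delays recovery; for death it makes the drug look protective. An ever/never comparison of symptom length by Mann-Whitney test has the same flaw.

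The missing date also affects the immunological objectives. An acute sample may be drawn at any time in a four-week window, and the listed fields do not show whether it came before or after treatment.

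**Working it through.** The plan states no figure for this point. The 10000 subjects in section 13 are an expectation, not the result of a power calculation. The check is therefore whether the bias arises under no treatment effect, and how large it is.

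**From the documents:** Day 0 is the first positive test; follow-up is 18 months (548 days used); the treatment fields are as in footnote 6; expected enrolment is 10000; the significance level is 0.05 (two-sided assumed).

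**Assumed, because the documents give no values:** exponential time to recovery with median m of 14, 30 or 90 days; half of patients intended for treatment; start uniform over 0 to w days; treatment received only if not yet recovered; true hazard ratio 1.

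**Mechanism, by hand (m = 14, w = 10).** The recovery hazard is λ = ln 2 / 14 = 0.0495 per day, so 1/λ = 20.2 days. The mean start day among those actually treated is 1/λ − w·e^(−λw)/(1 − e^(−λw)) = 20.2 − 10 × 0.610/0.390 = 4.6 days. After starting, the remaining time again has a median of 14 days. The treated group's median from Day 0 should therefore be about 14 + 4.6 = 18.6 days, with no effect at all. Simulation gives 18.8 days treated against 10.1 days untreated.

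**Recovery hazard ratio with ever-treated fixed from Day 0, true value 1:**

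| Median recovery | w = 2 | w = 5 | w = 7 | w = 10 | w = 14 | w = 28 |
|---|---|---|---|---|---|---|
| 14 days | 0.92 | 0.81 | 0.75 | 0.69 | 0.63 | 0.51 |
| 30 days | 0.95 | 0.90 | 0.86 | 0.82 | 0.77 | 0.65 |
| 90 days | 0.98 | 0.96 | 0.95 | 0.92 | 0.90 | 0.83 |

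Simulation error is about 0.01. With w = 0 the ratio is 1.00 in every row. The treated share matters: at m = 14 and w = 10 the ratio is 0.78 with 20% intended for treatment and 0.50 with 80%.

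**False-positive rate at 10000 patients:** about 100% for m = 14 with w = 2 or 5; 47% for m = 90 with w = 5; 7% for m = 90 with w = 2.

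**Death:** with 10% mortality by day 28 and w = 10, fixed coding gives a hazard ratio of 0.69 for an inert treatment.

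**With start dates:** coding treatment as time-dependent returns the recovery hazard ratio to 0.99 to 1.01.

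**With a day-28 landmark and no start dates:** the ratio is 0.97 to 1.01 across the scenarios, provided all treatment began by day 28. The landmark keeps only patients unrecovered at day 28, a share of 0.5^(28/m): 0.5^2 = 25% at m = 14, 0.5^0.933 = 52% at m = 30 and 0.5^0.311 = 81% at m = 90. It says nothing about symptom length or death before day 28.

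**The case against.** Several parts of the opposing case stand.

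- **The plan does not say treatment is a time-dependent covariate.** Section 13 names no such covariate, and does not name recovery as a Cox endpoint. Dated vaccination and repeated serology are obvious candidates. A reader might infer that a written analysis has been made impossible; the documents support only that the listed fields rule out this coding for a main-objective exposure.
- **Treatment need not be fixed from Day 0.** Therapy is recorded at the acute visit, and the next visit is at 3 months ± 1 month. A landmark at day 28 needs no start date and works for later sequelae. However, the plan defines none, and it leaves early outcomes and acute samples unresolved.
- **The bias is conditional.** A reader might infer that treated patients will look slower to recover. That requires ever-treated coding from Day 0 and a delay in starting. The largest figures belong to a 14-day median, which is closer to acute illness than to long-term sequelae.
- **The eCRF may hold dates.** Footnote 6 is a summary line, and the eCRF manual mentioned in section 14.5 was not supplied. Other footnotes also omit dates that an analysis would need: footnote 13 gives vital status without a date of death. The finding is that the protocol does not specify a start date, not that none is collected.
- **Early deaths may be under-represented.** Section 11 requires at least one follow-up visit and allows late recruitment, while section 14.4 permits retrospective capture after death. The size of the mortality bias in this cohort is therefore unknown.

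A reader might also infer that dose and duration fields cannot describe monoclonal antibodies. The documents do not say how these are given, so that is not relied on here.

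**Conclusion.** The point holds as a gap in what the protocol specifies. Collecting exactly the fields in footnote 6 leaves treatment off the Day 0 axis, for an exposure named in a main objective and an outcome dated daily.

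The consequence depends on the analysis chosen. If ever-treated is coded from Day 0, the apparent effect of an inert treatment on recovery ranges from large (about 0.75 to 0.63 at a 14-day median, start windows of 7 to 14 days) through moderate (0.86 to 0.77 at 30 days) to small (0.95 to 0.90 at 90 days). It is close to 1 when treatment starts within a day or two and the outcome lasts months. For death the bias runs the other way.

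All durations, start windows and treated shares are assumptions; the direction does not depend on them as long as treatment starts after Day 0. Confounding by indication is not part of these figures.

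**What to change.** In footnote 6 and the eCRF, unless the eCRF already holds them, record the dates of first and last administration for each anti-COVID drug. If the dates are already there, only the footnote needs amending.

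In section 13:

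- list the time-to-event endpoints and the time-dependent covariates;
- enter treatment as time-dependent from its start date for symptom length and death;
- where the start date is missing, use a day-28 landmark, limited to outcomes after day 28 and stating the assumption that treatment began by then;
- class acute laboratory samples as taken before or after first administration.

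The cost is two date fields per drug and a little extra abstraction. Some dates will be missing, mainly in outpatients enrolled late, which is why the landmark fallback is needed. Since baseline data may be collected retrospectively, the fields should be settled before abstraction at each cohort. Adjustment for confounding by indication must be planned separately.

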epidemiological, clinical, microbiological, and genotypic aspects of population, environment and socioeconomic features. The project builds upon existing, and new largescale population cohorts in Europe (France, Germany, Spain, Italy, Belgium, Romania, Netherlands, Luxemburg, and Slovakia) and non-European countries (India, Perú, Ecuador, Colombia, Venezuela, Argentina, Brazil, Congo and Gabon) including SARS-CoV-2 infected and non-infected individuals of all ages and conditions. The primary aim of ORCHESTRA is the creation of a new pan-European cohort applying homogenous protocols for data collection, data sharing, sampling, and follow-up, which can rapidly advance the knowledge on the control and management of the COVID-19. ORCHESTRA will include SARS-CoV-2-negative individuals and thereby enable a prospective follow-up and an analysis of vaccination response. The cohort will involve all patients with SARS-CoV-2 infections including fragile individuals (children, elderly, transplanted, oncological, HIV infected, and those with Parkinson disease or rheumatologic disease) if followed up in one of the study Partners center. Within ORCHESTRA project, the Work Package 2 (WP2) aims to assess long-term sequelae in recovered COVID-19 individuals. The scope of the present protocol is to describe the procedures of the long-term follow-up of COVID-19 patients enrolled in ORCHESTRA cohorts.

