11. RECRUITMENT STRATEGY

Inpatients will be recruited by the study team at the treating hospital. Outpatients will be recruited by the study team in the emergency rooms, outpatient clinics, and through the coordination with regional primary care networks, who will offer the opportunity to enter the study to patients with active or previous COVID-19. This allows a broad recruitment of cases and the rapid inclusion of additional study centers in regional hotspots.

Patients will be followed up for up to 18 months after the SARS-CoV-2 infection diagnosis. The recruitment can take place at any time between the SARS-CoV-2 infection diagnosis and the end of the 18month follow-up, provided that the patient ensures at least one follow-up visit. Discharged inpatients as well as recovered outpatients will be invited to participate by a phone call (which will be repeated once in case of no reply). The screening/baseline data collection (including the informed consent process) can be carried out on the same day of a follow-up visit.

Before the first patient is recruited at a location, the responsible investigator ensures that all legal and regulatory requirements are met. Patients can revoke their consent to participate in the study without restriction at any time and at their own request, without giving reasons and without any consequences for their future treatment. In case of loss to follow-up, the previous follow-up assessments will be included in the data analyses. Patients will be recruited until January 2023 and followed-up until June 2023, allowing a partial follow-up for participants whose SARS-COV-2 infection occurred after January 2022.

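### The vaccine-acceptance item does not record whether a vaccine was offered, so refusal and lack of access cannot be told apart among unvaccinated participants

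*Combined protocol and SAP*

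**What the plan says.** Table 1 in section 3.2 has a row for vaccine acceptance and its reasons, marked at all five time-points from two weeks to 18 months. Footnote 21 defines it: "Was the vaccine accepted? Why not accepted (lack of trust in efficacy and/or safety; not useful in the specific case", and the list closes with "prefer someone else gets it before me". There is no answer for not offered, not eligible, advised to wait, or other.

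The only other vaccination variable is footnote 9: "SARS-CoV-2 vaccination: vaccine name, date of administration". Section 12 makes vaccination status a mandatory item at each follow-up visit. Neither records whether a dose was offered.

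The item serves a secondary objective in section 8: "To describe the relationship between risk perception of reinfection and the adherence to preventative measures over time after the SARS-CoV-2 infection, including vaccine acceptance". Footnote 19 measures the other side of that relationship: "Perceived risk of re-infection on a scale 0-10 (no risk- very high risk".

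Section 10 admits any age. Section 5 names, besides European countries, "non-European countries (India, Perú, Ecuador, Colombia, Venezuela, Argentina, Brazil, Congo and Gabon". Section 11 states "Patients will be recruited until January 2023 and followed-up until June 2023". Section 13 gives no denominator, coding rule or missing-data rule for this item. It says only that a missing-data strategy, including regression-based imputation, will be developed.

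**The concern.** Acceptance is a decision, and it can be observed only in someone who had a decision to make. The item asks about the decision without first establishing that there was one. An unvaccinated child below a licensing age, an adult in a country with no supply, and an adult who declined an appointment all have an empty vaccination record, and footnote 21 offers no distinct answer for the first two. They may be entered as not accepting, left blank, or recorded under the reason that vaccination is not useful in their case, which turns lack of access into an attitude.

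What is at stake is the meaning of the outcome in the risk-perception objective. Access can vary with age, country, calendar date and time since infection, and perceived risk of re-infection may vary with the same factors. Adjusting for those factors does not restore the distinction, because refusal and non-offer stay mixed within every stratum. Offer status not asked at the visit may not be reliably recoverable later.

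**Working it through.** The plan gives no acceptance, access or precision figure for this item, so there is nothing to reproduce. The check has two parts.

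**1. Can any listed variable separate refusal from non-offer?**

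- Footnote 9 (vaccine name and date) separates vaccinated from unvaccinated.
- Footnote 21 (accepted or not, three attitude reasons) does not identify non-offer.
- Age (footnote 2), recruiting centre (in the participant code, section 14.5) and time since the first positive test (footnote 1) are correlates of access, not a record of it.

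The ambiguity is confined to the unvaccinated, but within that group nothing listed resolves it.

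**2. What follows under each way of recording a never-offered person?** Let a be acceptance among those offered, u the share not offered, and c the share of the never-offered coded as not accepting, the rest being blank. If everyone offered answers, measured acceptance among those answering is a(1−u) / [(1−u) + cu]. All values of a and u below are assumptions; the documents supply none.

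*All coded as not accepting (c = 1).* The formula reduces to a(1−u). With a = 85%:

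| u | measured acceptance |
|---|---|
| 10% | 0.85 × 0.90 = 76.5% |
| 20% | 0.85 × 0.80 = 68% |
| 40% | 0.85 × 0.60 = 51% |
| 60% | 0.85 × 0.40 = 34% |

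*All left blank (c = 0).* The formula reduces to a, so 85% stays 85% at every u.

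*Link to risk perception when c = 1.* Multiply acceptance in each group by one minus that group's share not offered, then compare high with low perceived risk.

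| Acceptance if offered, low / high | Not offered, low / high | Measured, low / high | Difference (points) | Odds ratio |
|---|---|---|---|---|
| 75% / 85% | none | 75% / 85% | +10 | 1.89 |
| 75% / 85% | 20% / 20% | 60% / 68% | +8 | 1.42 |
| 75% / 85% | 30% / 10% | 52.5% / 76.5% | +24 | 2.95 |
| 75% / 85% | 10% / 30% | 67.5% / 59.5% | −8 | 0.71 |
| 80% / 80% | 20% / 20% | 64% / 64% | 0 | 1.00 |
| 80% / 80% | 30% / 10% | 56% / 72% | +16 | 2.02 |
| 80% / 80% | 10% / 30% | 72% / 56% | −16 | 0.49 |

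The fourth row, for example, is (0.595/0.405) / (0.675/0.325) = 0.71. Equal lack of access dilutes a real link and leaves a null one alone. Unequal lack of access can inflate, reverse or create one. When c = 0 and everyone offered answers, every row returns to its value among those offered.

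*Scale.* With the expected 10,000 participants all answering and acceptance of 80%, the 95% half-width is 1.96 × √(0.8 × 0.2 / 10,000) = 0.8 points. A shift of several points would not be hidden by sampling error, and more patients would not remove it.

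**The case against.** The strongest reply is that footnote 21 is a one-line note to a schedule, not the data-entry form. The eCRF and its completion manual (section 14.5) are separate documents and may contain a not-applicable code or skip logic. The word accepted also presupposes an offer: if people never offered a vaccine do not answer, a negative answer means refusal, and acceptance among those answering is not lowered. Both points stand. They limit what can be said about the consequence, but they do not put an offer variable into the protocol.

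A reader might infer that people without access are counted as non-accepters. The documents do not support that, because no coding rule is stated. The 76.5% and 51% figures hold only if every never-offered person is coded that way.

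A reader might also infer that a positive link with risk perception will appear where none exists. That does not follow either: the direction depends on how access differs between low and high perceivers, on which the documents are silent.

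It is also fair to say that vaccinated people are identifiable from footnote 9, that likely correlates of access are collected for stratification, and that section 12 does not name this item among the mandatory questionnaires, so it may not be asked of everyone. These points narrow the problem to unvaccinated participants who are asked. Within that group it remains.

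**Conclusion.** The point holds as a gap in what is collected. As the protocol is written, refusal and lack of access are indistinguishable among the unvaccinated, and the wording in section 8, "adherence to preventative measures over time after the SARS-CoV-2 infection, including vaccine acceptance", needs them apart.

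The size of the consequence is conditional. If never-offered people are coded as not accepting, acceptance is understated by a × u: 8.5 points at u = 10% and 34 points at u = 40% for an assumed a of 85%. The association can then move either way or not at all. If they are left blank, there is no downward bias by this route. The blanks still cannot be told from unanswered items, and imputation under section 13 could assign a decision to someone who never had one.

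Confidence is high that the item and the other listed variables lack an offer field. It is moderate on the consequence, because the eCRF is not among the documents. The objective is secondary and descriptive, and the main objectives on sequelae and re-infection are untouched. The change is worth making because it is cheap and analysis cannot supply the missing field afterwards.

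**What to change.** Add one question to footnote 21, asked at each visit: *Has a SARS-CoV-2 vaccine been offered to the participant by this visit?* Answers: yes; no, not available or not eligible; no, advised to wait; unknown.

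- Ask acceptance and reasons only if the answer is yes, and add *other* to the reasons. Keep the gate to offer alone: a gate on offered or eligible would let eligible but never-offered people into a denominator labelled as those offered.
- State in section 13 that acceptance and its relation to risk perception are reported among those offered, that the not-offered share is shown separately, and that acceptance is not imputed for people not offered.
- If the eCRF already holds such a field, citing it in footnote 21 and stating the denominator in section 13 is enough.

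The cost is one eCRF field, a protocol amendment with ethics review (sections 14.1 and 14.10), and a smaller denominator for this objective. For scale, assume all 10,000 answer, acceptance is 85% and 40% were not offered. The 95% half-width then goes from 1.96 × √(0.85 × 0.15 / 10,000) = 0.7 points to 1.96 × √(0.85 × 0.15 / 6,000) = 0.9 points. The change removes access from the outcome. It does not remove ordinary confounding between risk perception and willingness, which still needs adjustment.
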